9.2 Setting

9.2.1 Eligibility

Female and/or male adult patients with a diagnosis of CKD and T2D will be enrolled after the decision for treatment with finerenone has been made by the treating physician.

Patients who have been prescribed finerenone in accordance with existing label will be eligible for enrollment. Contraindications according to the local market authorization should be carefully considered.

Evidence of assessment of all eligibility criteria by the physician or a delegate, as well as enrollment of a patient in the study should be documented in the patient medical records.

9.2.1.1 Inclusion criteria

- Adult female or male patient (≥18 years old)
- Diagnosis of CKD associated with T2D
- Decision to initiate treatment with finerenone was made as per investigator's routine treatment practice
- Signed informed consent

9.2.1.2 Exclusion criteria

- Participation in an investigational study with interventions outside of routine clinical practice
- Contra-indications according to the local marketing authorization

9.2.2 Withdrawal

In this observational study, withdrawal from the study is independent of the underlying therapy and will not affect the patient's medical care. Each patient may withdraw from the study at any time without giving a reason. If a patient wants to terminate the study participation, no further data will be collected. In case a patient would like to withdraw the consent given earlier, s/he should inform his/her doctor and the site should document the withdrawal in the (electronic) Case Report Form (CRF) as well as in the patient medical records.

9.2.3 Replacement

Patients who drop out (e.g. withdrawal, lost to follow-up) will not be replaced.

9.2.4 Representativeness

The representativeness of the study population, with regard to the range of characteristics that are reflective of the broader target population, is addressed by the fact that the study will include typical patients, which constitute more heterogeneous populations than those participating in randomized

21785 FINE-REAL; V 1.0; 09 February 2022; based on template version 15

Page 18 of 48

clinical trials (e.g., wide range of age, ethnicity, and comorbidities). In addition, the inclusion of a representative sample of study sites (i.e. health care providers, hospitals, etc.) in terms of geography, practice size, and academic or private practice type is aimed for as a measure to enhance the generalizability of study results.

The patients documented in the study should be selected based only on eligibility according to a minimal set of selection criteria (sections 9.2.1.1 and 9.2.1.2). No further selection should be applied, thus increasing the generalizability of the study results. Physicians or delegates will be asked to sample consecutive patients whenever possible. This consecutive sampling approach is intended to reduce selection bias by the treating physicians or delegates as to whom to enroll in the study, especially with regard to factors that may be associated to the outcome or prognosis of those patients (e.g. demographic characteristics, multiple comorbidities, as well as concomitant medications), thus maintaining the observational character and enhancing the external validity of the study.

The sample of study sites should, ideally, reflect the distribution of treatment settings in each participating country in the background of the specific local health system. Nevertheless, the final sample of study sites will strongly depend on the willingness of investigators to participate in the study.

9.2.5 Visits

The investigator or a delegate documents an initial visit, follow-up visits and the end of observation/final visit for each patient in the Case Report Form (CRF). Initial and follow-up visits occur during routine practice, the study protocol does not define exact referral dates for those visits.

The observation period for each patient will be at least 12 months or the whole treatment period with finerenone if patient permanently discontinues treatment prematurely. Please note that during temporary finerenone treatment pauses of ≤ 6 months, the patient should stay in the study. In the context of this study, treatment pauses > 6 months are considered as permanent treatment discontinuation leading to end of observation. For such cases, the date of the first visit after a treatment pause of > 6 months should be considered as date for end of observation.

Premature end of therapy does not automatically imply end of documentation: the patient should be followed up at least 30 days after receiving the last finerenone therapy.

Baseline or Initial visit

Once a patient is found eligible for inclusion, the investigator or designated staff will inform the patient about the study. Where applicable, this will include discussing the patient information sheet (PIS) and informed consent form (ICF) and asking the patient to read and – when agreeing to participate – sign the informed consent.

Baseline information (considered as data collected no more than 1 month prior to the 1st dose of finerenone) recorded with the status at initial visit before the first drug administration.

Follow-up visit(s)

It is assumed, that according to clinical practice, follow-up visits will happen approximately every 3 months during the 1st year of treatment and every 6 months thereafter.

21785 FINE-REAL; V 1.0; 09 February 2022; based on template version 15

Page 19 of 48

During that timeframe, each visit near this time points performed per routine clinical practice should be documented.

End of Observation/Final Visit

The final data collection (end of observation) is after 36 months or at the end of study (whatever is earlier).

At this final observation point, the patient's condition and a treatment assessment will be documented, including:

- Date of final data collection
- Date of last dose of finerenone
- Therapy status at end of observation

Primary reason for discontinuation of the observational study (if applicable) should be documented, i.e. patient lost to follow-up, consent withdrawn by patient, investigator decision, pregnancy, lack of efficacy, (Serious) Adverse Event/Adverse Drug Reaction, patient died, permanent treatment discontinuation of finerenone (non-administration of finerenone > 6 months) resulting in change of therapy (which therapy and reason for switch), center closed, study terminated by Bayer AG.

Lost to follow-up

A patient will be considered as 'lost to follow-up' if the last documentation of any information was 3 months prior to the planned observation period (end of study).

Typical information to be collected at the visits are summarized in Table 2.

Table 2: Tabulated overview on data collected according to the clinical routine practice during the study

	Baseline visit	Follow-up visit(s)	End of observation / Final visit
Date/type of visit	X	X	X
Eligibility/Informed Consent	X		
Demography	X		
Vital signs	X		
Disease history	X		
Co-morbidities (medical history, concomitant diseases)	X		
Concomitant medication	X	X	X
Exposure/treatment	X	X	X
Laboratory parameters	X	X	X
Adverse events	(X)	X	X*
Hyperkalemia	X	X	X
End of Observation			X
Healthcare resource utilization (inpatient/outpatient/emergency visits)	X	X	X
Diabetic retinopathy	X	X	X
Sampling of blood and urine samples for biobanking (for patients in the US only)**	X	X	X

^{*} Adverse events (up to 30 days after the final treatment with finerenone)

9.3 Variables

The investigator or a delegate collects study-relevant data for each patient (as described in section 9.4) and documents it in the Case Report Form (CRF). The CRF used for data collection in this study are kept as stand-alone documents (see Annex 1) and are available upon request.

9.3.1 Variables to determine the primary endpoint(s)

The variable for primary endpoint are:

• Clinical characteristics of underlying disease (CKD, T2D):

21785 FINE-REAL; V 1.0; 09 February 2022; based on template version 15

Page 21 of 48

^{**} For details, please refer to the corresponding stand-alone document (lab manual).

- History and diagnosis of CKD
- History and diagnosis of T2D
- Hypertension (resistant or non-resistant)
- O History of ischemic cardiovascular events such as:
 - Myocardial infarction
 - Acute coronary syndrome
 - Stroke
 - Percutaneous coronary intervention
 - Coronary artery bypass grafting
 - Peripheral artery disease including but not limited to event such as limb ischemia, claudication, limb ulcers or limb amputation
- Chronic heart failure
- Atrial fibrillation
- Diabetic retinopathy
- Reasons for introducing finerenone
- Reasons for discontinuation of finerenone
- Planned and actual duration of treatment with finerenone
- Dose and frequency of finerenone treatment
- Type, and duration of concomitant secondary therapies:

The following types of medication are considered to be relevant:

- Oral and injectable antidiabetic treatments
 - SGLT2i
 - GLP1-RA
 - DPP-4i
 - SU
 - Metformin
- Lipid lowering treatment
 - Statins
- Renin-angiotensin-system (RAS) inhibitors (including ARNI)
 - ACEi
 - ARB
 - ARNI
- o MRA¹
- Digoxin

_

21785 FINE-REAL; V 1.0; 09 February 2022; based on template version 15

Page 22 of 48

¹ Another MRA should not be given together with finerenone, however we are interested to know if a patient was exposed before the initiation of finerenone.

- Betablocker
- Diuretics
 - Loop
 - Potassium sparing
- Potassium supplements
- Potassium binders
- Herbal therapy
- Traditional Chinese medicine
- Anti-thrombotic treatment
 - Aspirin
 - Anticoagulants
 - Warfarin or VKA
 - DOAC
 - LMWH
- Vaccination against Sars-Cov2
- NSAID (including over the counter NSAID)

9.3.2 Variables to determine the secondary endpoints

The variables for secondary endpoints are:

- Occurrence of AEs/SAEs overall and by MedDRA PTs
- Occurrence of hyperkalemia
 - o Occurrence of hyperkalemia leading to study drug discontinuation
 - Occurrence of hyperkalemia leading to dialysis
 - o Occurrence of hyperkalemia leading to hospitalization

9.3.3 Variables to determine the further endpoints

- Reasons, frequency and duration of inpatient², outpatient and emergency visits
- Occurrence of newly diagnosed diabetic retinopathy or progression of existing disease at study entry

9.3.4 Patient characteristics/demography

- Year of birth
- Ethnic group
- Race (black/non-black)³

21785 FINE-REAL; V 1.0; 09 February 2022; based on template version 15

Page 23 of 48

² Inpatient visits are defined as ≥1 overnight stay

³ please note: assessment of this variable is essential for calculation of eGFR by CKD-EPI formula according to Levey et al. Ann Intern Med. 2009

- Sex
- Smoking habits and alcohol consumption
- Vital signs and physical examination
 - o Weight
 - o Height
 - Blood pressure

9.3.5 **Laboratory measurements**

Variables collected at baseline:

- Serum creatinine (last available value)
- eGFR value as determined by investigator and formula used for calculation of eGFR
- Liver function (last available value of AST and ALT)
- Hemoglobin (Hb) (last available value)
- Serum⁴ potassium (last available value)
- Serum sodium (last available value)
- HbA1c (last available value)
- Fasting blood glucose (last available value)
- At baseline only: UACR: date and result (value) of the most recent testing
- Result of urine test (last available recording)
 - Presence of blood
 - Presence of other sediments
 - Urinary tract infection (y/n)

Variables collected at post-baseline visits:

- Serum creatinine⁵
- Serum⁶ potassium
- Result of urine test:
 - Presence of blood

⁴ Plasma values are also accepted.

⁵ Note that eGFR will be calculated by the EDC system.

⁶ Plasma values are also accepted.

- Presence of other sediments
- Urinary tract infection (Y/N)

9.4 Data sources

The investigator or a delegate collects historic data (demographic and clinical characteristics) from medical records, or else by interviewing the patient. Likewise, the investigator or a delegate collects treatment related data during visits that take place in routine practice.

Each patient is identified by a unique central patient identification code, which is only used for study purposes. For the duration of the study and afterwards, only the patient's treating physician or authorized site personnel is able to identify the patient based on the patient identification code.

9.5 Study size

Global study

4000 patients are planned to be enrolled.

The aim of the study is to describe treatment patterns and to obtain useful estimates with adequate precision for safety outcome endpoints. The study is not aimed to confirm or reject pre-defined hypotheses. Therefore, the sample size was determined due to feasibility reasons.

Treatment patterns will be analyzed by using descriptive statistics, such as frequencies for categorical variables and sample statistics for continuous variables, as described in section 9.7.3 Confidence intervals are not applicable.

For the secondary endpoints incidence proportions, cumulative incidences and incidence rates will be estimated and corresponding two-sided 95% confidence intervals will be provided, as described in section 9.7.4.

With a sample size of 4,000 patients, for potential incidence proportions of 1%, 5%, 10% and 50%, respectively, the following precisions can be expected:

# of patients	Incidence proportion (%)	95% CI of incidence proportion	Width (%) of 95% CI
4,000	1%	(0.7%, 1.4%)	0.7%
	5%	(4.3%,5.7%)	1.4%
	10%	(9.1%, 10.9%)	1.9%
	50%	(48.5%, 51.5%)	3.1%

The 50% incidence proportion maximizes the precision width, therefore, maximum width with 4,000 patients will not be greater than 3.1%.

Subset China

400 patients are planned to be enrolled from China. For potential incidence proportions of 1%, 5%, 10% and 50%, respectively, the following precisions can be expected:

# of patients	Incidence	95% CI of	Width (%) of
	proportion (%)	incidence	95% CI
		proportion	
400	1%	(0.0%, 2.0%)	2.0%
	5%	(2.9%, 7.1%)	4.3%
	10%	(7.1%, 12.9%)	5.9%
	50%	(45.1%, 54.9%)	9.8%

The 50% incidence proportion maximizes the precision width, therefore, maximum width with 400 patients will not be greater than 9.8%.

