8.1 Primary objective

The primary objective in this study is to describe treatment patterns in patients with CKD and T2D treated with finerenone in routine clinical practice.

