9.7.3 Analysis of primary endpoint(s)

Descriptive statistics will be used to analyze the following variables assessing the treatment patterns relating to finerenone:

- Reasons for introducing/discontinuing finerenone
- Planned and actual duration of treatment with finerenone
- Dose and frequency of finerenone treatment
- Actions taken after finerenone introduction (e.g continue treatment, addition of second therapy, interrupt treatment, discontinue treatment)
- Actions taken after finerenone interruption (e.g restart finerenone alone, introduce concomitant therapy, discontinue finerenone)
- Treatment pathways for secondary medications after introduction of finerenone,

Type, dose and duration of prior and concomitant therapies

Frequencies will be provided in summary tables along with graphical summaries such as sunburst plots.

Continuous variables will be summarized in tables with the appropriate measures (mean, median, SD, IQR).

More details will be provided in the SAP.

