9.7.4 Analysis of secondary endpoints

The analysis of the secondary endpoints will be of a descriptive nature. The use of endpoint refers to the secondary endpoints described in section 9.1.2.

The following metrics will be provided:

- Number and proportion of subjects with endpoint
- Number of occurrences of the endpoint
- Incidence rates of the endpoint per 100 patient-years

In addition, AEs will be classified by MedDRA PT using the latest version of MedDRA. A summary of AEs will be presented by primary System Organ Class (SOC) and Preferred Term (PT). Aggregate frequencies at the SOC level will be presented.

For hyperkalemia frequency tables will be provided and cumulative incidences will be provided in the form of Aalen-Johansen estimates and curves, given adequate data is available. More details will be provided in the SAP.

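### Section 9.5 wrongly calls confidence intervals inapplicable to the primary treatment-pattern results; the effect is small overall but larger in subsets and for treatment duration

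*Protocol*

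**What the plan says.** Section 8.1 makes treatment patterns the primary objective. Section 9.1.1 builds the primary endpoint from clinical characteristics, reasons for starting and stopping finerenone, planned and actual treatment duration, dosing and concomitant therapy.

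Section 9.5 says that these will be described by frequencies and sample statistics, and adds: "Confidence intervals are not applicable". Section 9.7.3 follows this. For categorical variables, "Frequencies will be provided in summary tables along with graphical summaries such as sunburst plots"; for continuous variables it lists mean, median, SD and IQR. No interval estimate is mentioned.

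The next paragraph of section 9.5 treats the other endpoints differently: "For the secondary endpoints incidence proportions, cumulative incidences and incidence rates will be estimated and corresponding two-sided 95% confidence intervals will be provided". The same section states the precision aim for safety only: "to obtain useful estimates with adequate precision for safety outcome endpoints". It then tabulates expected 95% interval widths, with maxima of 3.1 points at N=4,000 and 9.8 points for China at N=400.

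**The concern.** A confidence interval expresses the sampling error of an estimate. It does not need a hypothesis to test, and the protocol accepts this by giving intervals for the secondary endpoints of a study that tests nothing. Section 9.2.4 asks for consecutive patients and a representative spread of sites so that results generalise. Proportions and durations meant to generalise carry sampling error whether they are labelled primary or secondary.

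The split also separates closely related quantities. Hyperkalemia leading to discontinuation is a secondary endpoint and gets an interval. The reasons for discontinuation are part of the primary endpoint and get none.

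This is a stated rule, not a detail left open for the SAP: an SAP that added intervals for treatment patterns would depart from section 9.5. At stake is how readers judge the primary results where denominators are small or follow-up is incomplete.

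**Working it through.** **Inputs.** From section 9.5: N=4,000 overall, 400 in China, two-sided 95% level, stated maximum widths 3.1 and 9.8 points. From the list of countries at the front of the protocol: 18 countries. Assumptions not in the protocol: simple random sampling, the 3,600 non-China patients spread evenly over 17 countries, and 10% to 30% of patients discontinuing.

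**The plan's own figures.** The Wald half-width is h = 1.96 × √(p(1−p)/n). At p = 0.5:

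- N=4,000: 1.96 × √(0.25/4,000) = 1.55 points, so the width is 3.1.
- N=400: 1.96 × √(0.25/400) = 4.9 points, so the width is 9.8.

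Both stated maxima reproduce. The formula uses only p and n, so the tabulated widths apply equally to a treatment-pattern proportion on the full denominator.

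**Denominators relevant to the primary endpoint**, worst case p = 0.5:

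| Denominator | n | Half-width (points) |
|---|---|---|
| All patients | 4,000 | 1.55 |
| All discontinuers, 30% stop (assumed) | 1,200 | 2.8 |
| All discontinuers, 10% stop (assumed) | 400 | 4.9 |
| China | 400 | 4.9 |
| Average other country, 3,600/17 (assumed) | 212 | 6.7 |
| China discontinuers, 30% stop (assumed) | 120 | 8.9 |
| China discontinuers, 10% stop (assumed) | 40 | 15.5 |

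For a proportion of 10% the half-widths are 0.9 points at N=4,000 and 2.9 points at N=400.

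**Treatment duration.** If every duration were complete, the half-width for the mean would be 1.96/√n standard deviations: 0.03 SD at N=4,000 and 0.10 SD at N=400. They need not be complete. Section 9.1 recruits over about 30 months and ends the study 12 months after the last patient's first visit. Section 9.2.5 closes observation at 36 months or end of study, whichever is earlier. A patient still on finerenone at that point has a censored duration. The planned mean, median, SD and IQR do not show who was censored or when, so a reader cannot construct a valid interval for treatment duration from them.

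**The case against.** The best defence is that leaving out intervals is a consistent choice. Section 9.5 asks for description of treatment patterns and precision for safety, and sections 9.7.1 and 9.7.3 follow that division. Much of the primary endpoint is baseline characteristics and medication use, commonly tabulated without intervals. Absolute and relative frequencies are planned, so a simple interval for a proportion can be computed from the table, including for reasons for discontinuation. Section 9.5 already prints the worst-case widths. Intervals also say nothing about site selection, which section 9.2.4 admits will depend on investigators' willingness to take part. Most of this stands. It justifies planning no intervals for baseline description. It does not make them inapplicable to estimates that are meant to generalise, and it does not cover treatment duration.

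Two stronger readings are tempting, and the protocol supports neither.

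- A reader might infer that the study's main results are reported with no means of judging precision. The safety results do get 95% intervals, simple intervals for the primary proportions follow from the counts, and the full-sample uncertainty is small.
- A reader might infer that the secondary intervals are themselves left undefined, because section 9.5 refers to section 9.7.4 and the metrics there, beginning with "Number and proportion of subjects with endpoint", name no interval. But section 9.5 makes the commitment outright ("corresponding two-sided 95% confidence intervals will be provided"), while section 9.7.4 excludes nothing and leaves further detail to the SAP. At most the cross-reference is imprecise; section 9.7.4 needs no change on this account.

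**Conclusion.** The sentence in section 9.5 is wrong as a statement of method, and its effect is minor. On the full sample the missing interval is at most about ±1.55 points and can be derived by any reader. It is up to ±4.9 points in China. In smaller countries it would be around ±6.7 points under an even spread, but section 9.7.1 analyses countries separately only if numbers suffice and there is a local need. For reasons for discontinuation the size depends on how many stop, which the protocol does not state: ±2.8 to ±4.9 points overall and ±8.9 to ±15.5 points in China, if 10% to 30% do.

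All these figures are worst cases at p = 0.5 and assume independent patients. Clustering within sites or countries would widen them: an assumed design effect of 2 turns 1.55 into about 2.2 points and 4.9 into about 6.9. Treatment duration is the clearest loss, because its interval cannot be recovered from the planned summaries. No hypothesis test depends on any of this, and no data are lost.

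**What to change.** Replace the sentence in section 9.5 with a statement to this effect: no confidence intervals are planned for baseline description; two-sided 95% intervals will accompany the key treatment-pattern estimates, both overall and in the China and country tables. Those estimates are:

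- the proportion discontinuing finerenone;
- the main reasons for discontinuation, with the number of discontinuers shown as the denominator;
- the starting dose;
- treatment duration, estimated by a method that handles patients still on treatment at the end of observation.

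Add a matching line to section 9.7.3. The interval formulas can be left to the SAP.

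The cost is a wording change, slightly more table output and one decision on how to handle censored durations. No extra data or visits are needed. The tables should note that the intervals reflect sampling error only and not the selection of sites.

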Within the randomized, double-blind, multicenter phase III trial FIGARO-DKD trial, 7,437 patients with CKD and T2D were randomized 1:1 to receive finerenone or placebo. Of those, 7,352 patients were available for analysis (n= 3,686 patients in the finerenone and n= 3,666 patients in the placebo arm). Among patients with T2D and stage 2 to 4 CKD with moderately elevated albuminuria or stage 1 or 2 CKD with severely elevated albuminuria, finerenone therapy led to a significant reduction in the incidence of cardiovascular events, defined as a composite of death from cardiovascular causes, nonfatal myocardial infarction, nonfatal stroke, or hospitalization for heart failure, as compared with placebo (HR, 0.87; 95 % CI, 0.76 to 0.98; P=0.03). The overall frequency of adverse events did not differ substantially between groups. Cases of hyperkalemia occurred more frequently with finerenone than with placebo (10.8 % vs. 5.3 %), and more finerenone-treated patients were hospitalized or discontinued the study due to hyperkalemia than placebo-treated patients (0.6 % and 1.2 % vs. 0.1 % and 0.4 %, respectively). However, none of these adverse events resulted in death [10].

Based on these study results, first marketing authorization for finerenone was granted by the US Food and Drug Administration (FDA) in July 2021 for the treatment of adults with CDK associated with T2D. The study will be initiated after the local approval at participating countries. Since all available safety and efficacy data were gathered from controlled clinical trials, real-world

experience from clinical routine is missing. The FINE-REAL study aims at collecting real-world data and providing insights into the use of finerenone in routine clinical setting. In China's Mainland, the approval of finerenone 10/20 mg [OAD] in T2D and CKD patients will be granted with a potential request for a post-authorization commitment study. China's Mainland is added to the FINE-REAL study to fulfill this request.

8. Research questions and objectives

The aim of this study is to provide insights on characteristics and treatment patterns of patients with CKD and T2D treated with finerenone in routine clinical practice.

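### Section 9.5: the global 1% precision row does not fit its own table, and the China 1% row is a Wald interval at 4 expected events whose upper limit is too low

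*Protocol*

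**What the plan says.** Protocol section 9.5 states that "4000 patients are planned to be enrolled" and that "400 patients are planned to be enrolled from China". It gives as part of the aim "to obtain useful estimates with adequate precision for safety outcome endpoints", and says that for the secondary endpoints "corresponding two-sided 95% confidence intervals will be provided". Each of the two tables is introduced with the words "for potential incidence proportions of 1%, 5%, 10% and 50%, respectively, the following precisions can be expected". No interval method is named.

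The stated rows are:

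| Assumed proportion | Global, n = 4,000 | Width | China, n = 400 | Width |
|---|---|---|---|---|
| 1% | 0.7 to 1.4 | 0.7 | 0.0 to 2.0 | 2.0 |
| 5% | 4.3 to 5.7 | 1.4 | 2.9 to 7.1 | 4.3 |
| 10% | 9.1 to 10.9 | 1.9 | 7.1 to 12.9 | 5.9 |
| 50% | 48.5 to 51.5 | 3.1 | 45.1 to 54.9 | 9.8 |

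The text concludes that the "maximum width with 4,000 patients will not be greater than 3.1" percent, and that the "maximum width with 400 patients will not be greater than 9.8" percent. Section 9.5 also says that the sample size was set by feasibility.

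Section 9.1.2 lists hyperkalemia leading to drug discontinuation and hyperkalemia leading to hospitalization among the secondary endpoints. Section 7 gives finerenone-arm rates for them from the second cited phase III trial: more finerenone patients were "hospitalized or discontinued the study due to hyperkalemia than placebo-treated patients (0.6 % and 1.2" percent, respectively. The first cited trial has 2.3% for discontinuation due to hyperkalemia.

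**The concern.** Two printed rows deserve a check. In the global table the 1% row has an upper limit and a width that do not seem to come from the calculation behind the rows below it. In the China table the 1% row is symmetric about 1% and reaches down to 0.0%, as a normal approximation does when very few events are expected.

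The 1% rows are the ones closest to the rare hyperkalemia outcomes. If their limits are wrong, a reader judging whether 400 patients give adequate precision for those outcomes gets too favourable a picture, above all of how large a risk the data could rule out. Section 7 says that China's mainland was added to meet a potential request for a post-authorization commitment study, so a regulator may read this table.

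**Working it through.** **Inputs.** n = 4,000 and n = 400; proportions 1%, 5%, 10% and 50%; two-sided 95% (all from section 9.5). Cited rates 0.6%, 1.2% and 2.3% (section 7). z = 1.96.

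**Step 1: reproduce the China table.** Wald: p ± z·√(p(1−p)/n).
- 1%: 1.96 × √(0.01 × 0.99/400) = 0.975 points, so 0.025% to 1.975%, width 1.95. Stated: 0.0 to 2.0, width 2.0.
- 5%: 2.86% to 7.14%, width 4.27. Stated: 2.9 to 7.1, width 4.3.
- 10%: 7.06% to 12.94%, width 5.88. Stated: 7.1 to 12.9, width 5.9.
- 50%: 45.10% to 54.90%, width 9.80. Stated: 45.1 to 54.9, width 9.8.

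All four rows are Wald, and the 9.8% maximum reproduces.

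**Step 2: reproduce the global table.** Same formula, n = 4,000.
- 5%: 4.33% to 5.68% (4.325 to 5.675 before rounding), width 1.35. Agrees.
- 10%: 9.07% to 10.93%, width 1.86. Agrees. Clopper-Pearson and Wilson both give an upper limit of 10.97%, which would print as 11.0.
- 50%: 48.45% to 51.55%, width 3.10. Agrees.
- 1%: 1.96 × √(0.01 × 0.99/4000) = 0.308 points, so 0.69% to 1.31%, width 0.62. This prints as 0.7 to 1.3, width 0.6. Stated: 0.7 to 1.4, width 0.7. **Does not agree.**

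Other methods for the 1% row (40 of 4,000):

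| Method | Interval | Width |
|---|---|---|
| Clopper-Pearson | 0.72 to 1.36 | 0.64 |
| Wilson | 0.74 to 1.36 | 0.62 |
| Agresti-Coull | 0.73 to 1.36 | 0.63 |
| Jeffreys | 0.73 to 1.35 | 0.62 |

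The first three print as 0.7 to 1.4. (Jeffreys is 1.345% before rounding and prints as 1.3.) All four widths print as 0.6. The stated 0.7 equals the difference of the rounded limits, 1.4 − 0.7. The other rows do not follow that convention: it would give 10.9 − 9.1 = 1.8 and 51.5 − 48.5 = 3.0, where 1.9 and 3.1 are stated.

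**Step 3: the China 1% row by other methods (4 of 400).**
- Clopper-Pearson: 0.27% to 2.54%, width 2.27.
- Wilson: 0.39% to 2.54%, width 2.15.
- Wald, as stated: 0.03% to 1.98%, width 1.95.

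The stated upper limit is about 0.5 to 0.6 points too low.

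**Step 4: exact coverage of a nominal 95% Wald interval at n = 400.** Sum the binomial probabilities of all counts whose interval contains the true proportion. The Wald upper limits at 0, 1 and 2 events are 0%, 0.74% and 1.19%.

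| True rate | Counts whose upper limit is below it | Probability | Counts whose lower limit is above it | Coverage |
|---|---|---|---|---|
| 0.6% | 0 | 9.0% | 0.3% | 90.7% |
| 1.0% | 0 to 1 | 9.1% | 0.3% | 90.7% |
| 1.2% | 0 to 2 | 14.1% | 0.4% | 85.5% |
| 2.3% | 0 to 4 | 4.7% | 0.6% | 94.7% |

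Nearly all misses near 1% are intervals that lie below the true risk. At 0.6%, 1.0% and 1.2%, Clopper-Pearson covers 98.9%, 96.1% and 96.8%, and Wilson 96.5%, 93.2% and 96.8%.

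For contrast, Wald coverage at n = 400 is 92.7% at 5%, 94.3% at 10.8% and 94.5% at 18.3%; the last two are the overall hyperkalemia rates in section 7. At n = 4,000 it is 93.1% at 0.6% and 94.2% at 1.2%.

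**Step 5: the China maximum width by method (200 of 400).** Wald 9.80, Wilson 9.75, Jeffreys 9.77, Clopper-Pearson 10.02.

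**The case against.** The strongest reply is that these are planning illustrations. Section 9.5 speaks of potential proportions and expected precision, the sample size rests on feasibility, the study tests no hypothesis, and section 9.7.1 leaves statistical details to the SAP. Nothing says that Wald intervals will be used for the reported results, so the coverage figures describe the planning table and not a committed analysis. That stands. It is why the choice of analysis method is not part of this point and why the point is minor. It does not make the printed rows right.

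A second reply is that the global 1% limits are valid exact or Wilson limits, that the width follows if rounded limits are subtracted, and that the discrepancy is under 0.1 point. Each part is true. But neither the method nor the rounding convention is the one used in the rows beside it.

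Three stronger readings are tempting, and the document does not support them:
- A reader might infer that the 9.8% China maximum is understated. It reproduces under Wald and holds under Wilson and Jeffreys. Of the intervals in step 5, only Clopper-Pearson exceeds it, and the protocol does not commit to that method.
- A reader might infer that Wald fails across all the cited hyperkalemia rates. It does not: coverage is 94.7% at 2.3% and close to nominal at 10.8% and 18.3%.
- A reader might take the 0.0% lower limit in the China row as a true zero. It is 0.025% shown to one decimal.

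**Conclusion.** The point holds for the two 1% rows. The global row combines an interval that is not Wald with a width that no method in step 2 gives from unrounded limits, in a table whose other rows are Wald with widths from unrounded limits. The error is 0.1 point in the upper limit or the width, depending on the method intended. The China row is a correctly calculated Wald interval in a setting where Wald is unreliable. Its upper limit of 2.0% should be about 2.5%, and coverage at the cited rates of 0.6% and 1.2% is about 91% and 86%.

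This assumes simple binomial proportions with all 400 or 4,000 patients in the denominator, and takes the cited trial rates only as a guide to what the study may see. The remaining rows and both stated maximum widths stand under the method used. Severity is minor: no sample size, endpoint or conclusion changes.

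**What to change.** Choose one interval method suited to low proportions, name it beside the two tables in section 9.5, recompute every row with it, and take all widths from unrounded limits. Either of these sets would do (limits in %, width in brackets):

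| Proportion | China, Clopper-Pearson | China, Wilson | Global, Clopper-Pearson | Global, Wilson |
|---|---|---|---|---|
| 1% | 0.3 to 2.5 (2.3) | 0.4 to 2.5 (2.2) | 0.7 to 1.4 (0.6) | 0.7 to 1.4 (0.6) |
| 5% | 3.1 to 7.6 (4.5) | 3.3 to 7.6 (4.3) | 4.3 to 5.7 (1.4) | 4.4 to 5.7 (1.4) |
| 10% | 7.2 to 13.4 (6.1) | 7.4 to 13.3 (5.9) | 9.1 to 11.0 (1.9) | 9.1 to 11.0 (1.9) |
| 50% | 45.0 to 55.0 (10.0) | 45.1 to 54.9 (9.8) | 48.4 to 51.6 (3.1) | 48.5 to 51.5 (3.1) |

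The sentence on the China maximum width changes to 10.0% only if Clopper-Pearson is chosen; under Wilson it stays as it is. The global maximum of 3.1% stands either way. The cost is a table correction in one section, with slightly less favourable China figures at the low rates and no effect on design or enrolment.
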